6.5.3. Protocol deviations

Important deviations from the protocol and validity findings and the resulting assignment of subjects to the analysis sets (see Section 3) are agreed upon in the blind review meeting (BRM). The documentation of important deviations, validity findings and the assignment of subject data to analysis sets will be performed according to the sponsor's applicable Standard Operating Procedures and/or Instruction Manuals. The definition for important deviations and validity findings will be provided in the 'Specification of assessment criteria and identification requirements' before unblinding the data.

Identification of important deviations and validity findings will be done periodically while the study is running, concluding with the completion of the final list during the BRM. Any

version 3.0 Page: 83 of 87

changes to the statistical analysis prompted by the results of BRM will be documented in an amendment and, if applicable, in a supplement to this SAP.

The list of important deviations and validity findings will only be final after assessment of conditional findings, which are validity findings that can only be identified after unblinding of study treatment.

6.5.4. Medical history

For medical history the MedDRA (current version at the time of analysis) will be used. Medical history findings (i.e., previous diagnoses, diseases or surgeries) not pertaining to the study indication, starting before start of treatment and considered relevant to the study will be tabulated by primary SOC and PT by treatment group and overall. Medical history will be presented for SAF.

All new or worsened findings after start of study treatment should be documented on the AE eCRF page.

6.5.5. Prior, concomitant and post-treatment medication

[figure not shown]
For prior/concomitant/post-treatment medications, the following definitions in accordance with the Global Standards Catalogue (v4.0 or later) will be used in the analysis (see Figure 6–1):

- Prior medication: Medication taken before start of the study drug intake, (regardless of when it ended).
- Concomitant medication: Medication taken during treatment phase, i.e. between first and last study drug intake (regardless of when it started or ended).
- Post-treatment medication: Start of medication is after last study drug intake.

Partially missing dates will be imputed as described in Section 4.1.1.

version 3.0 Page: 84 of 87

Categories are prior medication (A, B, C), concomitant medication (B, C, D, E) and post-treatment medication (F). Source: Global Standards Catalogue V4.0

Medication, recorded as prior, concomitant or post-treatment medication in the eCRF, will be coded according to the World Health Organization Drug Dictionary WHODRUG Global (current version at the time of analysis), to the respective Drug Codes with their corresponding Anatomical Therapeutic Chemical (ATC) classification. In addition, prior, concomitant or post-treatment adjuvant endocrine therapy will be shown by ATC classification and Standardized Medication Name.

The number of subjects taking prior, concomitant or post-treatment medication will be analyzed using frequency tables and shown by treatment group. Analysis of prior, concomitant and post-treatment medication will be done on the SAF.

version 3.0 Page: 85 of 87

6.6. Appendix 6: Coding conditions applicable for AESI

	ing conditions applicable for AESI
AESI	Search
Potential AESI – Liver event	SMQ Cholestasis and jaundice of hepatic organ
	SMQ Drug related hepatic disorders – severe events only
"Any condition triggering close	SMQ Liver related investigations, signs and symptoms
liver observation" according to	SMQ Liver-related coagulation and bleeding disturbances
protocol Section 10.5 results in	
true AESIs of liver events. The	In addition, include AESIs ticked at AE-CRF.
search specified here is beyond	
the protocol definition of the AESI	
and will be considered together	
with the assessment by the Liver	
Safety Monitoring Board to	
determine a true AESI.	
Somnolence or fatigue	a) Somnolence MLG:
	PT Somnolence
	PT Hypersomnia
	b) Fatigue (MGL Decreased general strength and energy)
	PT Asthenia
	PT Decreased activity
	PT Fatigue
	PT Fatigue management
	PT Mental fatigue
	PT Physical deconditioning
	PT Sluggisheness
	In addition to MLGs above, include PT Sleep disorder due to general
	medical condition, hypersomnia type
Phototoxicity	BMQ Photosensitivity reactions
-	•
Post-menopausal uterine bleeding	
	MLG Female genital tract bleeding
	PT Abnormal uterine bleeding
	PT Abnormal withdrawal bleeding
	PT Cervix haematoma uterine
	PT Cervix haemorrhage uterine
	PT Coital bleeding
	PT Haematocoele female
	PT Haematosalpinx
	PT Haemorrhagic ovarian cyst
	PT Ovarian haematoma
	PT Ovarian haemorrhage
	PT postmenopausal haemorrhage
	PT Unexpected vaginal bleeding on hormonal IUD
	PT Uterine haematoma
	PT Uterine haemorrhage
	PT Vaginal haematoma
	PT Vaginal haemorrhage
	PT Vulval haematoma
	PT Vulval haematoma evacuation
	PT Vaginal haemorrhage
	PT Withdrawal bleed
İ	

version 3.0 Page: 86 of 87

7. References

- Arimidex SmPC. UK Summary of Product Characteristics for Arimidex(Anastrozole), dated 22 Jun 2021. 2021.

SAP (incl. version and date): V3.0 08 MAY 2024

Compound Number: BAY 3427080 / elinzanetant

Sponsor Name: Bayer Consumer Care AG

Legal Registered Address: [name]

Regulatory Agency Identifier Number(s):

Registry ID

EudraCT 2020-004908-33

Date: 25 OCT 2024

Version: 1.0

Confidential

The information provided in this document is strictly confidential and is intended solely for the performance of the clinical investigation. Reproduction or disclosure of this document, whether in part or in full, to parties not associated with the clinical investigation or its use for any other purpose without the prior written consent of the sponsor is not permitted.

Throughout this document, symbols indicating proprietary names (®, TM) may not be displayed. Hence, the appearance of product names without these symbols does not imply that these names are not protected.

This Statistical Analysis Plan is produced on a word-processing system and bears no signatures. The approval of the Statistical Analysis Plan is documented in a separate signature document.

Statistical Analysis Plan supplement BAY 3427080 / 21656 version 1.0

Page: 2 of 3

Table of Contents

Tit	le Page	1
T al	ble of Contents	_
1 a	ble of Contents	. . Z
1.	Supplementary analyses to complement pre-planned analyses	3

version 1.0 Page: 3 of 3

1. Supplementary analyses to complement pre-planned analyses

This supplementary analysis is being conducted to be able to differentiate possible safety events during placebo-controlled phase (week 1-12) vs. when all subjects received elinzanetant 120 mg (week 13 onwards).

To address this, the following additional analyses will be contacted.

• Tables and figures representing liver monitoring (Section 4.5.3.4.1 in the SAP v3.0) will be shown by week 1-12 and by treatment group (elinzanetant 120 mg and placebo) and by week 1-52 (elinzanetant 120 mg). In addition, exposure adjusted incidence rates per 100 person-years will be calculated.

Formula for exposure adjusted incidence rate = (number of participants with event / sum of exposure days) * 100.

Where sum of exposure days = sum of time to first event for participants if an event occurred + sum of treatment duration with time after treatment up to end of observation for participants without event. Results are provided per 100 person-years, where one person-year is defined as 365.25 days.

- Tables for the following (Sections 4.5.3.6, 4.5.3.7, 4.5.3.9 in the SAP v3.0):
 - Breast imaging Mammogram/Ultrasound
 - o Transvaginal ultrasound
 - Endometrial biopsies

will be shown by treatment group, in addition end of treatment (EoT) and unscheduled visit will be divided into week 1-12 and week 13-52.

version 2.0 Page: 1 of 3

Title Page

Protocol Title: A double-blind, randomized, placebo-controlled multicenter study to investigate efficacy and safety of elinzanetant for the treatment of vasomotor symptoms caused by adjuvant endocrine therapy, over 52 weeks and optionally for an additional 2 years in women with, or at high risk for developing hormone-receptor positive breast cancer

Protocol Number: 21656

SAP (incl. version and date): V3.0 08 MAY 2024

Compound Number: BAY 3427080 / elinzanetant

Sponsor Name: Bayer Consumer Care AG

Legal Registered Address: [name]

Regulatory Agency Identifier Number(s):

Registry ID

EudraCT 2020-004908-33

Date: 09 DEC 2024

Version: 2.0

Confidential

The information provided in this document is strictly confidential and is intended solely for the performance of the clinical investigation. Reproduction or disclosure of this document, whether in part or in full, to parties not associated with the clinical investigation or its use for any other purpose without the prior written consent of the sponsor is not permitted.

Throughout this document, symbols indicating proprietary names (®, TM) may not be displayed. Hence, the appearance of product names without these symbols does not imply that these names are not protected.

This Statistical Analysis Plan is produced on a word-processing system and bears no signatures. The approval of the Statistical Analysis Plan is documented in a separate signature document.

Statistical Analysis Plan supplement BAY 3427080 / 21656 version 2.0

Page: 2 of 3

Table of Contents

Tit	le Page	.1
Tal	ble of Contents	.2
1.	Supplementary analyses to complement pre-planned analyses	.3

Page: 3 of 3

version 2.0

1. Supplementary analyses to complement pre-planned analyses

This supplementary analysis is being conducted to be able to differentiate possible safety events during placebo-controlled phase (week 1-12) vs. when all subjects received elinzanetant 120 mg (week 13 onwards).

To address this, the following additional analyses will be contacted.

• Tables and figures representing liver monitoring (Section 4.5.3.4.1 in the SAP v3.0) will be shown by week 1-12 and by treatment group (elinzanetant 120 mg and placebo) and by week 1-52 (elinzanetant 120 mg). In addition, exposure adjusted incidence rates per 100 person-years will be calculated.

Formula for exposure adjusted incidence rate = (number of participants with event / sum of exposure days) * 100.

Where sum of exposure days = sum of time to first event for participants if an event occurred + sum of treatment duration with time after treatment up to end of observation for participants without event. Results are provided per 100 person-years, where one person-year is defined as 365.25 days.

- Tables for the following (Sections 4.5.3.6, 4.5.3.7, 4.5.3.9 in the SAP v3.0):
 - Breast imaging Mammogram/Ultrasound
 - o Transvaginal ultrasound
 - Endometrial biopsies

will be shown by treatment group, in addition end of treatment (EoT) and unscheduled visit will be divided into week 1-12 and week 13-52.

In addition, adverse events (AEs) related to abuse potential, including drug abuse and dependence, as well as drug withdrawal, that occur while on-treatment and post-treatment will be presented. AEs will be categorized by primary System Organ Class (SOC) and Preferred Terms (PTs) for Week 1-12, 13-26, 27-52 and overall week 1-26 and 1-52 by study drug. Ontreatment AEs are defined as AEs with an onset between first and last study drug intake date. For abuse potential, post-treatment AEs are all AEs with an onset after the last study drug intake date. Events are assigned to the study drug the participant received last.

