4.5.3.4.1. Liver monitoring

The following parameters will be investigated in addition to the standard lab presentations:

- Aspartate aminotransferase (AST) (in U/L),
- Alanine aminotransferase (ALT) (in U/L),
- Alkaline phosphatase (ALP) (in U/L),
- Total Bilirubin in serum (in mg/dL)
- International normalized ratio (INR).

Frequency tables presenting number and percentage of subjects by treatment group for baseline and post-baseline (both scheduled and unscheduled measurements can be used), will be presented for the following categorizations (where ULN stands for "Upper Limit of Normal"):

- For ALT and AST, separately:
 - $\circ \ge 1 \times ULN, \ge 3 \times ULN, \ge 5 \times ULN, \ge 8 \times ULN, \ge 10 \times ULN, \ge 20 \times ULN$
- For ALT and AST combined (if at least one of ALT and AST falls into the category):
 - $0 \ge 3 \times ULN, \ge 5 \times ULN, \ge 8 \times ULN, \ge 10 \times ULN, \ge 20 \times ULN$
- For Total bilirubin:
 - $\circ \ge 1 \times ULN, \ge 2 \times ULN, \ge 5 \times ULN, \ge 8 \times ULN$
- For ALP:
 - $\circ \geq 1.5 \times ULN, \geq 2.0 \times ULN, \geq 3.0 \times ULN$
- For INR:

version 3.0 Page: 53 of 87

$\circ \geq 1.5, \geq 2$

Frequency tables presenting number and percentage of participants by treatment group for post-baseline will be presented for the following combinations of ALT/AST and Total bilirubin or INR,

Relative to ULN:

- ALT or AST $\ge 3 \times ULN$ and $\ge 1.5 \times ULN$ in Total bilirubin
- \circ ALT or AST $> 3 \times ULN$ for and $> 2 \times ULN$ in Total bilirubin
- o ALT or AST $\ge 3 \times ULN$ followed by $\ge 2 \times ULN$ in Total bilirubin (measured within 30 days afterwards) (Hy's Law criteria).
- ALT or AST $\ge 3 \times ULN$ and ≥ 1.5 for INR
- ALT or AST \geq 5×ULN for more than 2 weeks
- o ALT or AST ≥8×ULN
- o ALT or AST \geq 3×ULN with the appearance of any signs or symptoms based on close liver observation eCRF page.
- ALP $\ge 2 \times ULN$ and Total Bilirubin $\ge 2 \times ULN$

Relative to baseline (BL):

- ALT $\ge 3 \times BL$ or AST $\ge 3 \times BL$ and Total bilirubin $\ge 2 \times BL$
- ALT $\ge 3 \times BL$ or AST $\ge 3 \times BL$
- \circ ALT $\geq 5 \times BL$ or AST $\geq 5 \times BL$
- ALT $\ge 2 \times BL$ or AST $\ge 2 \times BL$ and Total bilirubin $\ge 2 \times BL$
- ALP $\ge 2 \times BL$ and Total bilirubin $\ge 2 \times BL$

Time to event analysis

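### SAP supplement 2.0 sets out to separate Weeks 1-12 from Week 13 onwards, but its liver displays use Weeks 1-12 and Weeks 1-52, so the later period is not shown separately for the main liver outputs

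*SAP*

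**What the plan says.** Section 1 of SAP supplement 2.0 gives its purpose as being able to "differentiate possible safety events during placebo-controlled phase (week 1-12) vs. when all subjects received elinzanetant 120 mg (week 13 onwards"). Three sets of displays follow, each with its own windows:

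- **Liver monitoring (SAP 4.5.3.4.1).** Tables and figures "will be shown by week 1-12 and by treatment group (elinzanetant 120 mg and placebo) and by week 1-52 (elinzanetant 120 mg"). Exposure-adjusted incidence rates per 100 person-years are added. Supplement 1.0 uses the same wording.
- **Breast imaging, transvaginal ultrasound and endometrial biopsy.** The "end of treatment (EoT) and unscheduled visit will be divided into week 1-12 and week 13-52".
- **Adverse events related to abuse potential.** These are shown "for Week 1-12, 13-26, 27-52 and overall week 1-26 and 1-52 by study drug".

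In SAP 4.5.3.4.1 itself, the tables of multiples of the upper limit of normal (ULN) are described as "Frequency tables presenting number and percentage of subjects by treatment group for baseline and post-baseline". The tables combining ALT/AST with bilirubin or INR are described as "Frequency tables presenting number and percentage of participants by treatment group for post-baseline". Neither has a split by week.

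**The concern.** The supplement poses a two-part contrast. For the liver displays it supplies the first part and an overall total, but not the second part. The imaging and biopsy tables get disjoint windows. The abuse-potential events get disjoint windows plus totals. Only the liver displays have no window that starts at Week 13.

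Raised liver enzymes are a listed risk (protocol 2.3.1) and an adverse event of special interest (AESI; protocol 8.3.6), and they have a dedicated monitoring board (protocol 10.1.3). Whether elevations cluster early, persist or first appear late is what a reader would want from a split at Week 12. Setting a Week 1-12 column beside a Week 1-52 column does not answer this directly, because the second column partly repeats the first.

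**Working it through.** **1. Windows side by side (supplement 2.0)**

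| Display | Week 1-12 | A window starting at Week 13 | Overall |
|---|---|---|---|
| Liver tables, figures, rates | yes, by arm | none | 1-52, elinzanetant |
| Imaging, ultrasound, biopsy (EoT and unscheduled visits) | yes | 13-52 | not stated |
| Abuse-potential AEs | yes | 13-26, 27-52 | 1-26, 1-52 |

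The overlap concerns elinzanetant data only. Placebo data from Weeks 1-12 are not part of the Week 1-52 elinzanetant column.

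**2. Does the main SAP fill the gap?** Not for the threshold displays. The tables in 4.5.3.4.1 are post-baseline by treatment group, and the liver injury plots use each woman's maximum post-baseline value, which discards timing.

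**3. How much of Weeks 1-52 is Weeks 1-12?** Inputs from the sample size sections (protocol 9.2, SAP 5): 270 and 135 randomised, 10% dropout in the first 3 months, and 30% yearly dropout in the elinzanetant arm. These reproduce the plan's retention figures: 270 × 0.9 = 243; 135 × 0.9 = 121.5, stated as about 122; 270 × 0.7 = 189. Assumptions of this review: linear loss between these points; switched women retained as in the elinzanetant arm (122 × 189/243 = 94.9 at Week 52); the Week 1-52 column includes switched women.

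- Elinzanetant arm, Weeks 1-12: (270 + 243)/2 × 84/365.25 = 59.0 person-years
- Elinzanetant arm, Weeks 13-52: (243 + 189)/2 × 280/365.25 = 165.6
- Switched women, Weeks 13-52: (122 + 94.9)/2 × 280/365.25 = 83.1
- Total: 307.7. Share from Weeks 1-12: 59.0/307.7 = 19.2%

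With no dropout, in person-weeks: 270 × 12 = 3,240 of 3,240 + 270 × 40 + 135 × 40 = 19,440, or 16.7%. If the column held the elinzanetant arm alone, the share with dropout would be 59.0/(59.0 + 165.6) = 26.3%.

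**4. What this does to a rate.** The documents give no liver event rates, so these are assumed values, in events per 100 person-years. Weeks 1-52 rate ≈ 0.192 × (Week 1-12 rate) + 0.808 × (Week 13-52 rate).

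| Weeks 1-12 | Weeks 13-52 | Weeks 1-52 reads |
|---|---|---|
| 8 | 2 | 3.15 |
| 2 | 2 | 2.00 |
| 2 | 4 | 3.62 |

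The total lies above, at or below the later rate according to whether the hazard falls, stays constant or rises.

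**5. Can the later period be obtained by subtraction?** Only in part. Suppose 6 women on elinzanetant had an event in Weeks 1-12 and 10 in Weeks 1-52. Then 10 − 6 = 4 had a first event after Week 12. The number with any event after Week 12 could be anything from 4 to 10, because a woman with events in both periods is counted once.

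**The case against.** The strongest reply is that much of the later liver information is planned elsewhere.

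- The liver AESI is driven by thresholds. It covers any condition triggering close liver observation (protocol 8.3.6), with criteria such as ALT or AST above 3 × ULN (protocol 10.5.1), and results leading to close observation are to be reported as adverse events (protocol 10.5.2). SAP 4.5.2 summarises AESIs in the same way as treatment-emergent events, which have columns for Weeks 13-26 and 27-52.
- High and low laboratory abnormalities have the same columns (SAP 4.5.3.4).
- Cumulative-incidence curves for first ALT or ALP of at least 3 × ULN, and individual time courses for women meeting close-observation criteria, show timing (SAP 4.5.3.4.1).
- First events after Week 12 can be obtained by differencing if counts and person-time are printed.
- Pairing a clean placebo-controlled window with all elinzanetant exposure is a defensible choice for sparse events. The displays are descriptive, and the liver board reviews cases individually.

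Most of this stands. It rules out two stronger statements that a reader might infer: that Week 13 onwards is never shown for liver safety, and that nothing planned reveals whether elevations continue, fade or appear late.

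It does not close the gap. The AESI search is wider than the protocol definition (SAP 6.6) and is not a table of laboratory thresholds. High/low flags are not ULN multiples. The curves cover only ALT and ALP, not bilirubin or the combinations. Differencing yields first events only. None of these is a Week 13 onwards version of the threshold, combination, plot or rate displays that the supplement itself lists to meet its aim.

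**Conclusion.** The point holds in a limited form. The liver windows in supplement 2.0 do not deliver the contrast it states. Week 13 onwards is not shown separately for the ULN-multiple tables, the Hy's Law and other combination tables, the liver injury plots or the exposure-adjusted rates. The overlap is about 19% of planned Week 1-52 elinzanetant person-time. That figure rests on planned retention, linear loss and equal retention in switched women. It uses treatment time only, whereas the supplement's denominator stops at a first event and, for women without one, adds time after treatment.

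A reader might infer that the Week 1-52 rate overstates the later rate. The documents do not support that: they give no event rates, the direction depends on the hazard, and the column is labelled Weeks 1-52 and does not claim to estimate the later period. No hypothesis test is affected. The change is worth making because the mismatch is with the supplement's own aim and is cheap to remove.

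**What to change.** In the liver item of the supplement:

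1. Add a Week 13-52 window to the tables, figures and exposure-adjusted rates of SAP 4.5.3.4.1, as the same supplement does for imaging and biopsy.
2. Preferably show that window by original arm (continuing elinzanetant, switched from placebo). The split goes beyond the stated aim, but it avoids mixing the first weeks on drug of switched women with the later exposure of continuing women.
3. State when time at risk starts in that window, and whether a woman with an event in Weeks 1-12 can be counted again.
4. Keep Weeks 1-52 as the overall elinzanetant total.

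The cost is a sentence or two in the supplement and a few more descriptive columns, many with sparse events, from data already collected. Trial conduct and confirmatory testing are unchanged.

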Time to event: The randomization date (for randomized but not treated subjects) /start of study treatment (for treated subjects) will be used as the start date for the calculation of time to event. Therefore, the time of event will be defined as "date of event – randomization date (for randomized but not treated subjects) / start of study treatment (for treated subjects) +1".

Unscheduled Assessments: Extra assessments (e.g. laboratory data or vital signs) associated with non-protocol visits will be included in listings, but not in the summary tables or figures, unless specified otherwise.

version 3.0 Page: 26 of 87

Definition of phases: The following phase definitions are used for displaying treatment duration, compliance, exposure and adverse events. The two phases in the Part A of the study represent the approximately first 12 weeks of the study, in which participants receive either placebo or elinzanetant 120mg and the approximately 14 weeks when all participants receive elinzanetant (i.e. the participants in the placebo arm will switch to elinzanetant). The start and end date of the phases is defined as following:

- Phase 1 (Part A):
 - Start date = start of treatment for treated subjects / randomization date for subjects, randomized, but not treated
 - \circ End date = first day of phase 2 study drug intake 1 day (based on the eCRF entry)

(For participants who stayed in the study for at least 12 weeks and received the phase 2 study drug);

OR

(For participants who have not received the drug phase 2 due to early discontinuation of randomized treatment or study withdrawal)

Week 12 assessment date or the post treatment phase end date, whichever is earlier

(this is for participants who discontinued from study drug but agreed to complete the assessments until Week 12)

or

Study drug discontinuation date or EoT assessment date, whichever is later (For participants who discontinued from randomized study drug before receiving phase 2 study drug and decided to go to the follow up period or withdraw from the study).

Note: HFDD morning diary and PRO questionnaires which were completed one day after the phase 1 end date will be assigned to phase 1. For participants who were randomized but not treated, the end date = randomization date.

- Phase 2 (Part A):
 - Start date = first day of phase 2 study drug intake (identified based on the eCRF entry)
 - End date = Visit T9 date (For participants who completed the phase 2/Part A, i.e. 26 weeks)
 or

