4.5. Safety Analyses

4.5.1. Extent of Exposure

The analyses described in this section will be presented for the SAF and the FAS.

Treatment duration will be defined as the number of days from the day of first study drug intake up to and including the day of last study drug intake and will be summarized using descriptive statistics by treatment group and by study drug. For the display by Week 1-12, the treatment duration ends on the end of treatment phase 1 or on the day of last study drug intake, whatever is earlier. For the display by Week 13-26, the treatment duration starts on the first day of treatment phase 2. For the display by Week 27-52, the treatment duration starts on the Visit T9 + 1. The duration of extension period (Part C) starts on the Visit T13 + 1. (As defined in Section 4.1.2.)

The extent of exposure to elinzanetant will be summarized as the total amount of study drug intake in grams and the average daily dose in mg using descriptive statistics per treatment group.

The compliance (as percentage) will be calculated as:

100 * Number of capsules taken / Number of planned capsules

The number of planned capsules is calculated as:

treatment duration * 2

All capsules, including the placebo capsules, will be counted. For participants who withdraw prematurely from the study drug, compliance will be calculated up to the time of last dose. The compliance will be summarized descriptively by treatment group. In addition, percent of compliance will be categorized into 3 groups, less than 80%, 80 to 120% and greater than 120%, and the categories will be summarized by treatment group and by study drug.

Treatment duration will be presented based on the data collected via the eCRF. If the date for end of exposure is not available in eCRF, the last day of drug intake from eDiary will be used to determine the end of exposure. Extent of exposure and compliance will be calculated and presented based on the ePRO daily instrument 'Study drug intake documentation' and on the eCRF 'Drug Accountability' and 'Drug Exposure' pages. The summaries for treatment duration, exposure and compliance will be presented for weeks 1-12, 13-26, 27-52 and overall, (i.e., for the entire 26 (Part A)/52 (Part B) weeks). Treatment duration, exposure and compliance summaries will be shown separately for Part C.

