4.5.2. Adverse Events

Adverse events (AEs) will be collected from the start of study intervention until the last follow-up. (Serious) Adverse event ((S)AEs) which are related to protocol required study procedures (e.g. (S)AE related to invasive study procedures) will be recorded as (S)AEs from the signing of the Informed consent form (ICF) (pre-treatment (S)AEs). Any medical occurrences/conditions that begin in the period between signing ICF and the start of study intervention, and which are not related to a protocol-required study procedure, will be recorded on the Medical History/Current Medical Conditions, not as AEs.

All AEs will be summarized using the Medical Dictionary for Regulatory Activities (MedDRA) preferred terms (PT) grouped by system organ class (SOC) (the current version at the time of analysis) and classified into pre-treatment AEs, treatment-emergent (TEAE) and post-treatment AEs. Pre-treatment and post-treatment AEs will be shown by treatment group. Descriptive analysis for TEAEs will be performed for Week 1-12, 13-26, 27-52 and overall week 1-26, 27-52 and 1-52 by study drug.

Incidences of TEAEs and TESAEs per 100 person-years will be summarized by study drug and by study period (weeks 1-12, 13-26, 27-52 and overall elinzanetant for weeks 1-26 and 1-52).

The rate per 100 person-years is calculated as

Rate per 100 person-years = number of subjects with an event / (total drug exposure in years / 100),

where 365.25 days are taken as one year.

A TEAE is defined as any adverse event occurring or worsening on or after the date of the first dose of study drug up to 14 days after the date of the last dose of study drug. AEs will be flagged as TEAE except for AEs for which there is clear evidence that the AE starts before date of first study drug intake (pre-treatment AEs) or after the date of last study drug intake + 14 days (post-treatment AEs).

If the severity of a previously reported event worsens or if the relationship to study intervention/protocol required procedures changes, two separate events should be reported.

Worsening of an AE is defined as follows:

- AE intensity is worsened (e.g. moderate to severe)
- AE changed to a serious event
- AE ends with death

In case an AE starts before the date of last study drug intake + 14 days and worsens after last study drug intake +14 days, it will be considered as two AEs, a TEAE and a post-treatment AE.

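### The liver exposure-adjusted incidence rate formula in the SAP supplements divides by days, so as printed it is 365.25 times lower than its per-100-person-years label

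*SAP*

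**What the plan says.** Section 1 of SAP supplement 1.0 (25 OCT 2024) and of supplement 2.0 (09 DEC 2024) adds further liver displays and announces a rate: "In addition, exposure adjusted incidence rates per 100 person-years will be calculated". Both versions then print the same definition: "Formula for exposure adjusted incidence rate = (number of participants with event / sum of exposure days) * 100".

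The denominator is built from days. Its first part reads "Where sum of exposure days = sum of time to first event for participants if an event occurred". For women without an event, the second part is treatment duration extended to the end of observation. SAP Section 4.5.1 counts treatment duration in days: "Treatment duration will be defined as the number of days from the day of first study drug intake".

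The paragraph closes with the reporting unit: "Results are provided per 100 person-years, where one person-year is defined as 365.25 days".

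SAP Section 4.5.2 gives the adverse event rate with exposure already in years: "Rate per 100 person-years = number of subjects with an event / (total drug exposure in years / 100"), followed by "where 365.25 days are taken as one year".

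On the time origin, SAP Section 4.1.2 (time to event) says that "start of study treatment (for treated subjects) will be used as the start date for the calculation of time to event". The supplements show liver results for weeks 1 to 12 by treatment group, and for weeks 1 to 52 under the single label elinzanetant 120 mg. They do not say whether that second display includes women randomized to placebo, who take elinzanetant only from week 13.

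**The concern.** The formula and its label give different quantities. Participants divided by days and multiplied by 100 is a rate per 100 person-days. The conversion to years is stated in words afterwards but is not applied in the formula. The error was carried unchanged from supplement 1.0 into 2.0.

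Liver events are an adverse event of special interest with their own monitoring board, and the supplements exist to separate events in the placebo-controlled phase from later ones. If the line were programmed as it stands, every absolute liver rate and every rate difference would be on the wrong scale under a person-years heading.

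The unstated population of the 52-week elinzanetant display raises a second question. If switched women are included and their clock starts at the first placebo dose, 12 weeks of placebo would count as elinzanetant time at risk.

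**Working it through.** The documents give no numeric value for this rate, so there is no figure to reproduce. The check is one of units, followed by an illustration.

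**Inputs**
- e, participants with an event: not given in the documents; 5 is assumed for illustration.
- D, exposure days: in days, from the supplement's definition and SAP Section 4.5.1.
- One person-year = 365.25 days: supplement Section 1 and SAP Section 4.5.2.
- Planned arm sizes 270 and 135: SAP Section 5. Full exposure of everyone randomized is assumed (84 days for 12 weeks, 364 days for 52 weeks), ignoring early stopping of the clock at an event and any post-treatment time.

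**Step 1. Formula against label**
- As printed: R_print = e / D × 100
- As labelled: R_label = e / (D / 365.25) × 100
- R_label / R_print = 365.25, for any e and D.

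**Step 2. Illustration with e = 5**

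| Display | D (days) | Person-years | As printed | Per 100 person-years |
|---|---|---|---|---|
| Elinzanetant, weeks 1-12 | 270 × 84 = 22,680 | 62.09 | 0.0220 | 8.05 |
| Placebo, weeks 1-12 | 135 × 84 = 11,340 | 31.05 | 0.0441 | 16.10 |
| Elinzanetant, weeks 1-52 | 270 × 364 = 98,280 | 269.08 | 0.0051 | 1.86 |

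**Step 3. Cross-check.** With the same D, the form used in SAP Section 4.5.2, e / ((D / 365.25) / 100), equals R_label.

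**Step 4. What is and is not affected.** In weeks 1-12 of the illustration, the ratio of elinzanetant to placebo is 0.5 on either scale. The difference in size is 16.10 − 8.05 = 8.05 per 100 person-years when labelled correctly, and 0.0441 − 0.0220, about 0.022, as printed.

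**Step 5. The clock, only if switched women are in the weeks 1-52 display.** Take 122 switchers (the SAP's expected number of placebo-arm women completing 12 weeks), full exposure, and no liver event during placebo.
- Placebo time added: 122 × 84 = 10,248 days = 28.06 person-years.
- Elinzanetant time: 270 × 364 + 122 × 280 = 98,280 + 34,160 = 132,440 days = 362.60 person-years.
- Total under the SAP clock: 28.06 + 362.60 = 390.66 person-years.
- Reduction of the 52-week rate: 28.06 / 390.66 = 7.2%.
- With all 135 placebo women switching: 135 × 84 = 11,340 days = 31.05 person-years of placebo; 98,280 + 135 × 280 = 136,080 days = 372.57 person-years of elinzanetant; 31.05 / 403.62 = 7.7%.

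**The case against.** The strongest reply is that the conversion is in the same paragraph. The rate is announced per 100 person-years before the formula, and the unit and the 365.25-day year are given after it, so a careful programmer would infer the missing step. This stands, and it limits the point to a defect in the written formula. It does not remove the defect, because the formula and the sentence that follows still give two different numbers.

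Several stronger readings are tempting, but the documents do not support them.

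- *That the reported liver rates are wrong by a factor of 365.* The documents contain no such rate and do not show how the outputs were programmed.
- *That the missing conversion is what prevents comparison with the rates in SAP Section 4.5.2.* The denominators differ anyway. Section 4.5.2 uses total drug exposure. The supplement stops the clock at the first event and adds post-treatment observation for women without one. Correcting the unit puts both on the same scale but does not make them the same measure.
- *That placebo time is counted as elinzanetant time.* The supplements do not say that switched women are in the weeks 1-52 display. Only the women randomized to elinzanetant take it for all 52 weeks, and the liver outputs in SAP Section 4.5.3.4.1 are presented by treatment group. Where supplement 2.0 wants results by drug received, as for abuse potential, it says so. On the other side, SAP Section 4.5.2 does use an overall elinzanetant grouping for weeks 1-52, so pooling is possible.
- *That early liver risk on elinzanetant is understated by about 31%.* That figure is 1 − 270 / (270 + 122) = 0.31. It applies only to the 12-week point of a pooled cumulative incidence curve, and only if no placebo woman has an event; with equal risk in both arms there is no understatement. The separate weeks 1-12 display by treatment group shows the randomized arm's early risk without switchers.

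**Conclusion.** The printed formula is wrong as written in both supplement versions. It yields a rate per 100 person-days, exactly 365.25 times below its label, and this rests on no assumption beyond the definitions in the documents. It is a drafting error with the intended unit stated nearby. Its consequence is confined to absolute liver rates and rate differences, and arises only if the line was programmed literally. Primary efficacy is untouched.

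The clock point is separate and held with lower confidence. The population of the 52-week elinzanetant liver display is not stated. If switched women are in it, the SAP's time-to-event rule would lower the 52-week rate by about 7%, given 122 switchers, full exposure and no placebo-phase events. Placebo-phase events counted in the numerator would offset this. If switched women are not in it, there is no dilution.

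**What to change.** In the supplement, replace the formula with: rate per 100 person-years = number of participants with event / (sum of exposure days / 365.25) × 100. Then check that the programmed liver outputs use this form. The cost is one line of text and a program check; a rerun is needed only if the outputs followed the printed line.

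Add one sentence stating whether women switched from placebo are in the weeks 1-52 elinzanetant liver display. If they are, start their clock at the first elinzanetant intake. SAP Section 4.1.2 already defines that date as the start of phase 2, so no new data are needed. The affected rates and curves need rerunning only if switched women were included with the earlier start date.
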